9.1 Monitoring of Source Data

During the experiment, CGM data and insulin dosing data will be automatically stored in the bionic pancreas device (from which it will be downloaded at intervals). All of the data will be combined in a single database that will be compared against the primary data files for integrity. The computer database will be backed up at least monthly and the backup media stored in a secure location.

Study staff will be encouraged to raise any concerns they may have or problems they have identified at any time. The site PIs, in consultation with the co-investigators, will decide a course of corrective action, and resolution or progress will be assessed regularly.

An audit of procedures, regulatory documentation, and a sample of participant files will be performed by a member of the University of Colorado or the Diabetes Research Center, as applicable, at least biannually. The audit will be conducted by a staff member who is not directly involved in the conduct of the study. This audit will include a review of regulatory documentation, such as IRB and FDA correspondence, and a review of participant files, including a review of consents, case report forms, and other data from study visits.

A numeric code will be substituted for the participants' personal identifying information in the study database, which will be password protected. The key linking the medical record number of the participant with the numeric code, along with case report forms, and all information that is personally identifiable, will be stored in password protected and user-limited electronic files. All electronic records will be kept in a password protected computer database. All printed computer data will be disposed of confidentially when no longer needed. Only the study staff will have access to the study database. Participants may not withdraw from the de-identified database, but they may elect to have the key linking their medical record to the de-identified database destroyed.

The study data will be shared with collaborators at Beta Bionics, Inc., but only in a form in which all personally identifiable information has been removed (e.g. combined database including BG values, record of insulin delivered by the device, and blood insulin levels). Shared data will be in the form of a database in which only a number identifies participants.

Participants may not withdraw their data, as it will be stored in non-personally identifiable form.

9.2 Safety Monitoring

This study is considered moderate risk. An external Data and Safety Monitoring Board (DSMB) will oversee the conduct of the study and review its results on a regular basis. Additionally, they will be informed of all serious adverse events and any unanticipated adverse device events that occur during the study. The DSMB will be informed if there are any changes to the study protocol that could significantly impact the safety or scientific validity of the study. A final DSMB meeting will convene after the completion of the study. Safety and efficacy data will also be reported to the IRB and FDA in compliance with applicable regulations.

Use of the bionic pancreas system by a participant in the study will be discontinued if any of the following occur:

- A participant experiences an episode of diabetic ketoacidosis (DKA) requiring hospitalization in the iLet arm.
 - Hyperglycemic events will be classified as DKA if all of the following are present:
 - Symptoms including but not limited to polyuria, polydipsia, nausea or vomiting
 - Serum ketones > 1.5 mmol/L or large/moderate urine ketones
 - Arterial blood pH < 7.30 or venous blood pH < 7.24 or serum bicarbonate < 15
 - Treatment provided in a healthcare facility
- A participant experiences an episode of severe hypoglycemia in the iLet arm. Severe hypoglycemia is defined as requiring the assistance of another person due to altered consciousness, and requiring another person to actively administer carbohydrate, glucagon or other resuscitative

actions. This means the participant was impaired cognitively to the point that they were unable to treat themselves, were unable to verbalize their needs, was incoherent, disoriented, and/or combative, or experienced seizure or coma. If plasma glucose measurements are not available during such an event, neurological recovery attributable to the restoration of plasma glucose to normal is sufficient evidence that the event was induced by a low plasma glucose concentration.

- The investigator believes it is unsafe for the participant to continue in the study
- A participant becomes pregnant
- The participant requests that the study be stopped
- If more than 1 participant must have their bionic pancreas use stopped for severe hypoglycemia or DKA during the bionic pancreas arm that is not due to deliberate inappropriate use of the iLet (i.e., any two participants with a single event each), study randomization will stop and a vote of the DSMB will be required to restart. All serious and unexpected events will be reported to the DSMB within 72 hours.

Study participation is voluntary, and participants may withdraw at any time. The investigator may withdraw a participant who is not complying with the protocol. For participants who withdraw, their data will be used up until the time of withdrawal. For participants using the iLet who withdraw, a study provider will help them transition to their own therapy safely.

In case of a recurring system malfunction or participant safety issue observed with multiple participants, the overall study will be suspended while the problem is diagnosed. The study may resume if the underlying problem can be corrected by a protocol or system modification that will not invalidate the results obtained prior to suspension.

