 - Investigators may consider starting MDI users at the "higher" glucose target setting. If the "higher" setting is used, wait ~2 days before moving down to the default target.
- Participants will complete Clarke's Instrument for Impaired Awareness of Hypoglycemia.
 - Participants with a score > 4 will be instructed to check BG at 2am for the first 2 nights using the iLet

5.6.1.2 Mid-period Follow Ups (Visits 3, 4, 6, and 7):

- Study staff may supervise the first site change via a video visit, as needed or requested based on participant's prior experience and comfort level
- All participants will have a virtual phone visit on Day 2 and Day 5 (+/-2 days) to assess device adaptation, glucose control, and to answer any questions the participant may have
- Study staff will query the participant for any adverse events and assess the participant's ability to follow protocol and, if applicable, use the device at this time.

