6.2 Primary endpoint

- Percentage of individuals with mean CGM glucose <183 mg/dL (corresponding to an estimated HbA1c of <8.0%) on days 3-14, by group.

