6.6 Sample Size Determination

No formal statistical power or sample size calculations have been done for this study. This study is primarily intended to be a feasibility trial to verify that the iLet can be managed by both primary care physicians, endocrinologists, and delivered through telehealth.

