6.7 Statistical Analyses

An intention-to-treat analysis will be performed. Descriptive statistics will be used to summarize patient characteristics and assessments. We will estimate the percentage of participants who have a mean sensor glucose <183 mg/dl in the iLet arms of all four groups (PC-IP, PC-TH, EN-IP, EN-TH), along with confidence intervals using the Clopper-Pearson method. The hypothesis is that there is no difference in the percentage of each group that meet this metric.

The primary analysis of the designated endpoints will be calculated on an intention-to-treat basis. In cases where an arm was not completed, we will use the available data from that arm in the data analysis. We will calculate percentages, means, standard deviations (and medians and interquartile ranges as appropriate), and ranges in descriptive analyses. Unless otherwise specified, continuous data will be summarized by presenting the number of non-missing observations, mean and standard deviation (SD) or median, minimum, and maximum. Categorical data will be summarized by presenting the number of patients and percentage for each category. We will use the t-test for comparisons of means for normally distributed outcomes and the Mann-Whitney U test for comparisons of medians on non-normally distributed outcomes between groups (PC-IP, PC-TH, EN-IP, EN-TH). We will use the paired t-test for comparison of means for normally distributed outcomes and the Wilcoxon Signed Rank test for comparisons of medians on non-normally distributed outcomes when comparing between iLet and usual care within groups. There will be no adjustments for multiple comparisons.

We may, in exploratory analyses, also stratify subjects for secondary analyses of the pre-specified endpoints by the following characteristics: sex, age, usual care insulin total daily dose, body mass index, baseline A1c, and use of CGM in usual care.

P-values can be displayed to aid interpretation, not for inference. Tables, figures and listings of all primary, secondary and safety endpoints will be created.

Data from periods when the bionic pancreas was not in use will be included, if available (Dexcom CGM data may not be available in some failure modes).

All questionnaire data (including quality of life data) for patients who have completed a minimum of 4 days with a device will be included. Results will be compared by Wilcoxon signed-rank test.

6.7.1 *Safety Analyses*

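### A participant who leaves before day 3 of the iLet arm has no data in the primary window, and section 6.7 does not say how that person counts, so the primary percentage can be biased upward

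*Combined protocol and SAP*

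**What the plan says.** Section 6.6 describes the study as primarily a "feasibility trial to verify that the iLet can be managed" by primary care and endocrinology and delivered through telehealth. The primary endpoint in section 6.2 is "Percentage of individuals with mean CGM glucose <183 mg/dL (corresponding to an estimated HbA1c of <8.0%) on days 3-14, by group". Days 1 and 2 do not count.

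Section 9.2 gives a discretionary ground for removal: "The investigator may withdraw a participant who is not complying with the protocol". Non-compliance is not defined and no timing limit is set. The next sentence reads: "For participants who withdraw, their data will be used up until the time of withdrawal".

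Sections 5.6.1.2 and 5.6.2.2 schedule calls on Day 2 and Day 5. At the mid-period contacts staff are to "assess the participant's ability to follow protocol and, if applicable, use the device at this time".

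On analysis, section 6.7 says: "The primary analysis of the designated endpoints will be calculated on an intention-to-treat basis". It adds: "In cases where an arm was not completed, we will use the available data from that arm in the data analysis". It also says: "Data from periods when the bionic pancreas was not in use will be included, if available". Section 6.7.2 tabulates discontinuations with reasons. The only minimum-data rule, 24 hours of CGM within days 3-14, stands under Exploratory Analyses in section 6.7.4. Section 4.1 expects 40 completers and allows up to 80 to be screened and enrolled.

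**The concern.** The trial asks whether people, including those who have never used a pump, can be started and managed on the iLet in primary care and by telehealth. A participant who cannot manage the procedures and leaves in the first two days is a negative answer to that question. The plan gives such a person no place in its main result. Data up to withdrawal are kept, but they fall outside the endpoint window, and the available-data rule has nothing to work on.

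The secondary and other endpoints in sections 6.3 and 6.5 include no measure of successful start or of retention, so the primary percentage carries the feasibility message largely alone. If early leavers are left out of it, a group that lost people at the start could look as good as one that kept everyone. Section 6.7 hypothesizes that the groups do not differ on this percentage, so uneven early loss could also hide a difference.

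**Working it through.** The documents give no power, dropout or error-rate figure to reproduce. The group size of 10 in each of four groups is consistent with the total: 4 × 10 = 40.

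**Step 1: can someone leave with no endpoint data?** Yes. The first scheduled call is on Day 2, the endpoint window opens on day 3, and section 9.2 sets no earliest time for withdrawal. Someone withdrawn at or after the Day 5 call would normally have some data in the window and would stay in under the available-data rule. The gap is confined to exits before day 3.

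**Step 2: does any section say how that person counts?** No. Section 6.7 names intention-to-treat but gives no rule for a participant without days 3-14 CGM. Applied to the primary endpoint, the 24-hour rule in section 6.7.4 would leave the person out.

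**Step 3: size in one group of 10.** Clopper-Pearson intervals, as in section 6.7. The level is not stated there, so 95% is assumed.

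| Leave before day 3 | Meet <183 among the rest | Left out | Counted as not meeting |
|---|---|---|---|
| 1 | 9 of 9 | 9/9 = 100% (66.4-100) | 9/10 = 90% (55.5-99.7) |
| 1 | 8 of 9 | 8/9 = 88.9% (51.8-99.7) | 8/10 = 80% (44.4-97.5) |
| 1 | 7 of 9 | 7/9 = 77.8% (40.0-97.2) | 7/10 = 70% (34.8-93.3) |
| 2 | 8 of 8 | 8/8 = 100% (63.1-100) | 8/10 = 80% (44.4-97.5) |

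If leavers are replaced until 10 complete and all 10 succeed, the result reads 10/10 = 100% (69.2-100). Keeping the replaced person in the denominator gives 10/11 = 90.9% (58.7-99.8) with one replaced, and 10/12 = 83.3% (51.6-97.9) with two.

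**Step 4: expected bias, allowing that leavers might have succeeded.** Let w be the share leaving before day 3, p the success rate among those who stay, and q the rate the leavers would have had. Leaving them out reports p, while the full group would give (1 − w)p + wq. The difference is w(p − q).

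For scale only, take the Adult Bridging study in Table 2 and assume that participant means are normally distributed:

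- p from the iLet with lispro or aspart, 155 (SD 13) mg/dl: Φ((183 − 155)/13) = 98.4%.
- q from usual care, 163 (SD 26) mg/dl: Φ((183 − 163)/26) = 77.9%.

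With w = 10% (one in ten):

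- q = p: 0 points.
- q = 77.9%: 0.10 × (98.4 − 77.9) = 2.1 points.
- q = 0: 0.10 × 98.4 = 9.8 points.

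With w = 20% the same three cases give 0, 4.1 and 19.7 points.

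**The case against.** The strongest reply is that the non-compliance clause does not cause the gap. A participant's own request, a positive pregnancy test or lost sensor data before day 3 leaves the same empty window, so deleting the clause would not close it. That stands, and it is why the remedy belongs in section 6.7 and covers every reason for leaving.

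A reader might infer that section 9.2 contradicts the intention-to-treat analysis, or that the percentage is inflated as a matter of fact. The documents support neither. Permission to withdraw concerns conduct, no section says early leavers are removed from the denominator, and intention-to-treat can be read as keeping them. What the text shows is an unanswered question. Because the endpoint is computed from CGM in the window, omission is the likely practical outcome, but it is not a stated one.

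A reader might also infer that removals will be more frequent among pump-naive iLet users. The iLet brings added tasks, so this is plausible, but no withdrawal rate is given. The described response to difficulty is education and supervised site changes, and exclusion criterion 2 already screens out people unable to comply safely. Removals would also be visible, since section 6.7.2 lists reasons for discontinuation. It does not call for a split by group, arm or day, and it does not alter the denominator.

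Finally, counting leavers as not meeting the threshold can over-correct. If they would have succeeded at 77.9%, the rule understates the glucose result by 0.10 × 77.9 = 7.8 points at w = 10%. That is fair as a statement about glucose. As a statement about feasibility, someone who does not reach day 3 has not been successfully started, and the sensitivity analysis shows the other end of the range.

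**Conclusion.** The concern holds as a gap in section 6.7 that can bias the primary percentage upward. For one early leaver in a group of 10 the bias is 0 to about 10 points, and about 2 points if that person would have done as well as prior usual care. Ten points per removal is the upper end, reached when the leaver would have failed and everyone else succeeds. The range assumes that leavers are dropped and would have done no better than those who stay. Neither the number of early leavers nor their likely outcomes can be taken from the documents. The prior-study rates are for scale only: that study mixed injection and pump users and reported days 3-7.

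The intervals for 9/9 and 9/10 overlap heavily, and section 6.7 says p-values are not for inference, so no formal test is at risk. What is at risk is the headline percentage in small groups, where a single person decides between 90% and 100%. The plan should be changed. The non-compliance ground itself is not shown to be an error.

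**What to change.** In section 6.7:

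- Define the primary denominator as all randomized participants in each group, including any who are replaced.
- Count anyone who leaves before day 3 of the iLet arm, for whatever reason, as not meeting <183 mg/dl.
- Add a sensitivity analysis restricted to participants with available days 3-14 data.
- Report withdrawals for non-compliance by group, arm and day as a feasibility result.

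In section 9.2, leave the withdrawal ground in place. Add that withdrawal for non-compliance does not remove a participant from the primary denominator and that, if the participant agrees, study CGM collection continues.

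This takes a few sentences and one extra analysis. Reported percentages may be slightly lower. The rule also counts as not meeting the threshold someone randomized to usual care first who leaves before ever starting the iLet. The available-data analysis and the report by arm and day let a reader see how much that matters.

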9.3 Adverse Event Reporting Guidelines

9.3.1 *Definitions*

An **adverse event** is defined as any untoward or unfavorable medical occurrence in a human participant including any abnormal sign (for example, abnormal physical exam or laboratory finding), symptom, or disease, temporally associated with the participant's participation in the research, whether or not considered related to the participant's participation in the research (modified from the definition of adverse events in the 1996 International Conference on Harmonization E-6 Guidelines for Good Clinical Practice).

Hypoglycemic events are recorded as Adverse Events (severe hypoglycemic event) if the event required assistance of another person due to altered consciousness, and required another person to actively administer carbohydrate, glucagon, or other resuscitative actions. This means that the participant was impaired cognitively to the point that he/she was unable to treat himself/herself, was unable to verbalize his/ her needs, was incoherent, disoriented, and/or combative, or experienced seizure or coma. These episodes may be associated with sufficient neuroglycopenia to induce seizure or coma. If plasma glucose measurements are not available during such an event, neurological recovery attributable to the restoration of plasma glucose to normal is considered sufficient evidence that the event was induced by a low plasma glucose concentration.

Hyperglycemic events are recorded as Adverse Events (severe hyperglycemic event) if the event involved DKA, as defined by the Diabetes Control and Complications Trial (DCCT) and described below, or in the

absence of DKA if evaluation or treatment was obtained at a health care provider facility for an acute event involving hyperglycemia or ketosis.

Hyperglycemic events are classified as DKA if all of the following are present:

- Symptoms such as polyuria, polydipsia, nausea, or vomiting;
- Serum ketones >1.5 mmol/L or large/moderate urine ketones;
- Arterial blood pH <7.30 or venous pH <7.24 or serum bicarbonate <15 ; and
- Treatment provided in a health care facility

The PIs, Site PI, and co-investigators will review any adverse events after each experiment to determine severity (serious or non-serious), expectedness (expected or unexpected) and relatedness (related, possibly related or unrelated). The study investigator will assess the relationship of any adverse event to be related or unrelated by determining if there is a reasonable possibility that the adverse event may have been caused by the study intervention.

To ensure consistency of adverse event causality assessments, investigators should apply the following general guideline when determining whether an adverse event is related:

Related: There is a plausible temporal relationship between the onset of the adverse event and the study intervention, and the adverse event cannot be readily explained by the participant's clinical state, intercurrent illness, or concomitant therapies; and/or the adverse event follows a known pattern of response to the study intervention; and/or the adverse event abates or resolves upon discontinuation of the study intervention or dose reduction and, if applicable, reappears upon re-challenge.

Possibly Related: Possibly related to the research means there is a reasonable possibility that the adverse event, incident, experience or outcome may have been caused by the procedures involved in the research (modified from the definition of associated with use of the drug in FDA regulations at 21 CFR 312.32(a)). Reasonable possibility means that the event is more likely than not related to participation in the research or, in other words, there is a $>50\%$ likelihood that the event is related to the research procedures

Not Related: Evidence exists that the adverse event has an etiology other than the study intervention (e.g., preexisting medical condition, underlying disease, intercurrent illness, or concomitant medication); and/or the adverse event has no plausible temporal relationship to study intervention.

Serious adverse event means any event temporally associated with the participant's participation in research that meets any of the following criteria:

- results in death
- is life threatening (places the participant at immediate risk of death from the event as it occurred)
- requires inpatient hospitalization or prolongation of existing hospitalization;
- results in a persistent or significant disability/incapacity
- results in a congenital anomaly/birth defect
- any other adverse event that, based upon appropriate medical judgment, may jeopardize the participant's health and may require medical or surgical intervention to prevent one of the outcomes listed above (examples of such events include allergic bronchospasm requiring intensive treatment in the emergency room or at home, blood dyscrasias or convulsions that do

not result in inpatient hospitalization, or the development of drug dependency or drug abuse).

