5.6.1.2.2 UC arm

- No modifications will be made to dosing regimens for participants in the usual care arm.
- Study staff will confirm the participant is wearing the study CGM, and answer any questions the participant may have about the CGM. They will remind the participant to replace the study CGM after 10 days.

5.6.1.3 Crossover Visit (Visit 5):

- At the end of the first study period (Day 14 [+2]), participants will return to the clinic and answer the post questionnaires for the study arm.
- A urine pregnancy test will be performed in participants of child-bearing potential. If the test is positive, the participant will be informed of the result and the next planned study arm will not proceed. The date of the last menstrual period will also be documented.
- Any changes to medications or medical history and any adverse events that may have occurred since the last study visit will be documented.

- All study devices applicable to the arm just completed will be downloaded
 - BP arm: iLet and study glucometer and ketone meter
 - UC arm: Dexcom G6 and study glucometer
- Participants will repeat psychosocial questionnaires (including quality of life, fear of hypoglycemia, diabetes distress).
 - Participants coming off of the BP arm will be asked to complete the Bionic Pancreas User Opinion Survey
- Participants will then start over with Day 1 procedures for the arm they are randomized to next. This may occur immediately, or within 14 days after the completion of the first arm.
 - If the participant is switching from usual care to bionic pancreas:
 - If using an insulin pump (EN group), their own insulin infusion pump will be stopped and disconnected if applicable, and its infusion set will be removed
 - If using MDI therapy (PC group), they will be instructed not to take any additional insulin injections once the bionic pancreas is started, unless instructed to do so by study staff
 - If the participant is switching from bionic pancreas to usual care, a provider (MD or NP) will review the last several hours of insulin dosing and assist the participant in resuming their usual care.
 - For participants whose usual care is MDI therapy:
 - If normal long-acting dose time is MORNING:
 - Morning study visit – take full dose at visit, take next day dose at usual time
 - Afternoon study visit – three quarters of normal dose at visit, take next day dose at usual time
 - If normal long-acting dose time is EVENING:

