- Supplies will be shipped to the participant in advance of the scheduled study start visit (Day 1 Visit immediately below). They will be instructed not to unpack any study materials until the scheduled telehealth visit. This will include a scale for measurement of weight, a home pregnancy testing kit, and supplies required for the study.
- All TH study visits will be completed using HIPAA compliant videoconferencing software.

5.6.2.1 Day 1 Visit (Visit 2):

- The body weight of the participant will be verbally self-reported by the participants, who will be instructed to use the scale provided.
- A urine pregnancy test in participants of child-bearing potential will be completed at home using the study-provided pregnancy test at the start of the first arm. Participants will be instructed to complete the pregnancy test during the virtual visit and to show result to study staff. If the test is positive, the participant will be informed of the result and the visit will be ended. The date of the last menstrual period will also be documented.
- Study staff will review any changes in the participant's medical history or medications to ensure continued eligibility, and any adverse events that may have occurred since their screening visit.

5.6.2.1.1 *Participants randomized to usual care:*

- Study staff will review supplies provided and the study procedures.
- Participants will be trained how to insert, maintain and use the Dexcom G6.
- The participants will wear a Dexcom G6 sensor and study staff will confirm they are doing it properly.

5.6.2.1.2 *Participants randomized to bionic pancreas:*

- Study staff will review supplies provided and the study procedures.
- Participants will be trained how to insert, maintain and use the Dexcom G6 CGM.
- The participants will wear a Dexcom G6 sensor and study staff will confirm they are doing it properly.
- Participants will be trained to use the iLet, including navigating the GUI, filling and installing

cartridges and inserting infusion sets.

- Participants will set up the iLet and insert the infusion set and study staff will confirm they are doing it properly.
- The control algorithm will be initialized with the participant's weight.
- If using an insulin pump (EN group), their own insulin infusion pump will be stopped and disconnected if applicable, and its infusion set will be removed.

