 - If necessary, a staff member will meet the participant to assist with troubleshooting. This meeting may be delayed until morning if the problem occurs overnight —in this case, the participant will use their own pump or use injectable insulin until a meeting is possible. A member of the study staff (within their scope of practice and under the supervision of the site principal investigator) may advise them on how to manage their diabetes in the interim. If necessary, the iLet device may be replaced. This may require shipping a new device to the participant. For participants in the telehealth arm, a new device will either be sent via express delivery or driven to the participant if feasible. Participants will be instructed to revert to usual care until they get the iLet.
- If there is a complete failure of the iLet operation and it is anticipated that restarting it will take more than an hour, or there is physical disconnection from the iLet that lasts longer than one hour, participants may revert to usual care using their own insulin pump or with insulin injections until the iLet can be brought back online with the help of study staff. In addition, frequent BG checks (every 2 hours and before meals) will be advised for any participant not receiving CGM data in this circumstance. Every effort should be made to correct the problem as soon as possible, which should almost always be within 24 hours
- Participants will be instructed to call the study team immediately, at any time of day or night, under any of the following circumstances:
 - They have questions or concerns
 - They want assistance troubleshooting the device
 - They have unexplained glucose over 300 mg/dL for greater than 90 minutes
 - They have ketones greater than 2.5 mmol/L (Large)
 - They have ketones greater than 0.6 mmol/L for more than 90 minutes
- If the sensor fails, it should be replaced. If the sensor is offline, participants will be instructed to self-check blood glucose at least every two hours and before meals.
 - If the sensor is offline for more than 4 hours, the sensor alerts as failed and should be replaced.

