6.4 Safety endpoints

- Frequency of adverse events
- Frequency of severe hypoglycemia
- Frequency of diabetic ketoacidosis, as defined within this protocol in Section 9.2.

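### Whether hyperglycemia or ketosis short of DKA is recorded as an adverse event depends on where care was given, and ketosis resolved remotely feeds no safety endpoint

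*Combined protocol and SAP*

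**What the plan says.** **Definitions.** Section 9.3.1 opens by defining an adverse event as "any untoward or unfavorable medical occurrence in a human participant including any abnormal sign", and goes on to include laboratory findings and symptoms. It then gives a specific rule for hyperglycemia, under the label of a severe hyperglycemic event. DKA is recorded, and so is an event in the "absence of DKA if evaluation or treatment was obtained at a health care provider facility for an acute event involving hyperglycemia or ketosis". DKA itself has four required criteria, one of which is "Treatment provided in a health care facility".

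**Handling of raised ketones.** Section 5.7.2 applies to the iLet arm in all groups. At 0.6 mmol/l or more, participants replace the infusion set, tell study staff and keep monitoring. They call the team at once if ketones exceed 2.5 mmol/L, or exceed 0.6 mmol/L for more than 90 minutes. Under 5.7.4, a study physician or nurse practitioner speaks directly with the participant when ketosis raises concern for DKA.

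**Data and endpoints.** For participants leaving the iLet arm, the in-person crossover visit (5.6.1.3) lists this download: "BP arm: iLet and study glucometer and ketone meter". Ketone meters are also downloaded at or after the final visit (5.6.1.4, 5.6.2.4). Section 6.1.2 lists blood glucose meter data and the number of and reasons for unscheduled visits and calls, but no ketone data. The safety endpoints in 6.4 are adverse events, severe hypoglycemia and "Frequency of diabetic ketoacidosis, as defined within this protocol in Section 9.2". Neither 6.3 nor 6.5 lists a ketone or contact endpoint.

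**The concern.** The specific rule turns on the site of care, not on what happened to the participant, while the protocol's own pathway for ketosis is designed to settle it by phone. A participant could exceed the level labelled large, change the set, speak to a provider and recover without meeting the rule.

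Hypoglycemia is treated differently. It has a daily survey item, an endpoint for symptomatic episodes and a CGM endpoint below 54 mg/dl, none of which depends on where the participant was seen. Ketosis has nothing equivalent.

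This matters because the PC group has never used a pump, so infusion-set failure is a new hazard for those participants. The plan also intends to say something about safety: the title names it, section 8 promises knowledge of safety in untested care models, and 6.7.4 looks for support that the iLet can be used safely in primary care and by telehealth. With no safety tests planned (6.7.1), readers will rely on the raw counts.

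**Working it through.** The plan gives no event rate or power calculation to reproduce (6.6). The check is first textual, then a labelled illustration.

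**Step 1: does the ketosis pathway lead to a facility?**

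| Element | In person | Telehealth |
|---|---|---|
| Mid-period follow-up | Virtual phone visits, Day 2 and Day 5 (5.6.1.2) | Same (5.6.2.2) |
| Raised ketones, iLet arm | Change set, inform or call staff (5.7.2) | Same text |
| Ketosis concerning for DKA | Provider speaks to participant (5.7.4) | Same text |
| Emergency referral | Staff judgment (5.7.4) | Same text |
| Scheduled visits | Start, crossover and final visits in person | All by video (5.6.2) |

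Only emergency referral or care the participant seeks independently clearly reaches a facility. Whether a study-clinic contact, a home visit or a video assessment counts is not stated.

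**Step 2: what is captured regardless of facility?** Time above 250 mg/dl and unscheduled cartridge or infusion-set changes are endpoints in 6.5. Neither measures ketosis, and unscheduled set changes also have other causes, such as a set falling out. The ketone meter and the contact reasons bear on ketosis directly, but feed no endpoint.

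**Step 3: effect on recorded counts.** There are 20 in-person and 20 telehealth participants (10 PC and 10 EN in each). Let p be the share with one non-DKA episode in the iLet arm, and a the chance that an episode reaches a facility. Both are assumptions. Expected recorded episodes per mode = 20 × p × a.

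At p = 10% there are 20 × 0.10 = 2 true episodes in each mode:

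| a in person | a telehealth | Recorded in person | Recorded telehealth |
|---|---|---|---|
| 0.50 | 0.50 | 1.0 | 1.0 |
| 0.50 | 0.25 | 1.0 | 0.5 |
| 0.25 | 0.50 | 0.5 | 1.0 |
| 1.00 | 0.00 | 2.0 | 0.0 |

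The first row shows no difference between modes, yet half the episodes are lost in both. The second and third rows reverse the direction. The last row is the extreme. With a = 0.50 v 0.25, the recorded gap runs from 20 × 0.05 × 0.25 = 0.25 episodes at p = 5% to 20 × 0.30 × 0.25 = 1.5 at p = 30%.

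**Step 4: how much can the DKA count say?** If no DKA occurs, the upper 95% Clopper-Pearson limit is 1 − 0.025^(1/n): 30.8% for n = 10 and 16.8% for n = 20. A zero DKA count in a group would be weak evidence of safety, so discarding a related and possibly more frequent signal loses information.

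**The case against.** The broad definition at the head of 9.3.1 can be read to cover symptomatic ketosis managed at home. The serious-event criteria mention events treated at home, adverse events are queried at every visit from Visit 2, and 5.7.2 requires all participant contacts to be documented. This has force, and it means that omission is possible, not certain. But the specific rule reads as the operating one for hyperglycemic events. If it is not, staff have two rules and no way to choose. Each practice type is a single site, so different readings would fall on the PC v EN contrast.

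A reader might infer that the rule makes telehealth look safer: "All TH study visits will be completed using HIPAA compliant videoconferencing software", whereas in-person participants can be seen. The documents do not support that. No section brings an in-person participant to a clinic for ketosis, and Step 1 shows a common pathway. The sentence "If necessary, a staff member will meet the participant to assist with troubleshooting" in 5.7.2 belongs to the instructions for an iLet technical fault, and names no facility. Remote participants could even be sent to emergency departments more often.

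It is also fair to object that ketone data are not free of ascertainment effects. Testing follows glucose above 300 mg/dl lasting more than 90 minutes, the alarm for this is optional, and calling is the participant's choice. That stands, and is why the added data should supplement the adverse-event count and not replace it.

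**Conclusion.** The point holds as a gap in recording. Under the specific rule in 9.3.1, ketosis or hyperglycemia resolved remotely may go unrecorded as an adverse event in any group, and no endpoint uses the data that would show ketosis directly.

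A difference by care mode is possible, since telehealth care is wholly remote and location helps decide assignment, but its size and direction cannot be established. The counts in Step 3 rest on assumed episode rates and facility use.

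Nor is this a flaw in a comparison on which the trial rests. The primary endpoint is the percentage with mean CGM glucose below 183 mg/dL, safety is descriptive, and care mode is not randomised. The change is a cheap improvement to safety reporting.

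**What to change.** - Keep 9.3.1 for regulatory reporting, say what counts as a health care provider facility, and reconcile the specific hyperglycemia rule with the general definition.
- List ketone-meter data in 6.1.2.
- Add to 6.4, summarised descriptively by group under 6.7.1, the number of participants and of episodes in the iLet arm with ketones ≥0.6 and >2.5 mmol/l. These are levels the protocol already uses, taken here only as reporting cut-offs. Add study-team contacts for hyperglycemia or ketosis from the contact log.
- Assign readings to the arm by date, because the telehealth text lists the download only after devices are returned at the end.
- Report these beside the AE and DKA counts, not in place of them. State that testing and calling are participant-initiated and that care mode is not randomised.

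The cost is wording in four sections (6.1.2, 6.4, 6.7.1, 9.3.1) and one more table. The meters, downloads and contact records already exist, and no clinical rule changes. The downside is a larger, less flattering event count.
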